5.3. Lifestyle Considerations

No specific requirements

5.4 Screen Failures

A screen failure occurs when a participant who has consented to participate in the study is not subsequently participating in the study.

A minimal set of screen failure information is required to ensure transparent reporting of screen failure participants. This includes

- demography: age, gender, education level, user profile
- eligibility criteria
- screen failure details: known explanation for failure
- and any concern related to study

As mentioned above, approximately up to 50 patients will be screened - per site/ therapeutic area - to ensure we can enrol 15 patients in the study.

Individuals who do not meet the criteria for participation in the study (screen failure) will not be rescreened.

6. Study Intervention(s)

The objective of collecting these data is to demonstrate that AIDAVA is capable to integrate - and curate - data generated by the patients, as well as data generated by the Health Care Providers (hospital staff and GP) and therefore ensure a complete view of the patient records. The data collected through the personal apps and medical devices will not be used for clinical decision making.

6.1 Personal Apps

Participants will be requested to use a specific personal app to capture personal information that could be of value in a longitudinal health record.

	Breast Cancer & CVD
Name	BrightFish
Data Captured	QALY questionnaire (local language): EQ-5D standard
Period of use/ Frequency	Once during Week 1 of the evaluation (for G1 and for G2)
Provider	BrightFish
Link	https://brightfish.com/solutions/ehealth/
Pricing	(in negotiation - maximum of 16 K for whole projects)
Instructions for use	Provided via HDI in training materials
Monitoring of compliance	Not needed as the value of the information collected by the personal
of use	app has not be identified as a key data element for the registry

6.2. Medical Devices (CVD patient only)

Device/app	Notes
BP monitor with Afib detection	Withings BPM Connect
Data Captured	Blood Pressure
Period of use/ Frequency	During the whole evaluation : 3 times a week / 3 times a day
	Afterwards - once a month/ 3 times a day
API Integration	API Guide
Google Fit app	For Android users
Apple Health app	For iOS users
Instruction for use	In case of issue with the value of BP : go to the GP
	In case of issue with the app or the device: go the RA
Instructions in case of defect	Request support from Research Associate
Disposal after end of study	Patient can keep it
	Note: patients withdrawing from the study should return the
	device to the Research Associate/ site
Monitoring of compliance of use	Research Associate

All device deficiencies (including malfunction, use error and inadequate labelling) shall be documented and reported by the investigator throughout the clinical investigation.

7. Participant Discontinuation/Withdrawal

7.1 Participant Discontinuation/Withdrawal from the Study

- A participant may withdraw from the study at any time at the participant's own request for any reason (or without providing any reason).
- A participant may be withdrawn at any time at the discretion of the investigator for behavioural, or compliance reasons.
- At the time of discontinuing from the study, the personal health data from the patient will be deleted in the same way it is done at the end of each generation. The endpoints entered by the patient as part of the evaluation, will be used, if there is consent form the patient (per Informed Consent Form).
- The participant will be permanently discontinued from the study intervention and the study at that time.
- If the participant withdraws consent for disclosure of future information, the sponsor may retain and continue to use any data collected before such a withdrawal of consent.
- If a participant withdraws from the study, the participant may request destruction of any samples taken and not tested, and the investigator must document this in the data collection and entry forms (REDCap).

7.2 Lost to Follow up

A participant will be considered lost to follow-up if the participant repeatedly fails to return for scheduled visits and is unable to be contacted by the study site.

The following actions must be taken if a participant fails to return to the clinic for a required study visit:

- The site must attempt to contact the participant and reschedule the missed visit as soon as possible, counsel the participant on the importance of maintaining the assigned visit schedule, and ascertain whether the participant wishes to and/or should continue in the study.
- Before a participant is deemed lost to follow-up, the investigator or designee must make every
 effort to regain contact with the participant (where possible, telephone calls, and if necessary, a
 certified letter to the participant's last known mailing address or local equivalent methods).
 These contact attempts should be documented in the participant's medical record.
- Should the participant continue to be unreachable, the participant will be considered to have withdrawn from the study.

In the AIDAVA assessment study, there is a risk of patient discontinuation because of the 16 to 18 months time lag between EPOCH 1 and EPOCH 3. To decrease the risk and keep the momentum / interest of patients we will issue regular newsletters (one page every 3 to 4 months). In case of an important discontinuation we might need to ask sites to recruit new patients for EPOCH 3.

In case of withdrawal, patients will be requested what they wish to do with the PHKG containing their data and available in the system; they will be able to receive these data or to request deletion of the PHKG in the same way that at the end of the study (see Section 4.4). In case of lost to follow-up, the PHKG of the related patient will be deleted at the end of the study.

8. Study Assessments and Procedures

- Study procedures and their timing are summarised in the SoA. Protocol waivers or exemptions are not allowed.
- Adherence to the study design requirements, including those specified in the SoA, is essential and required for study conduct.
- All screening evaluations must be completed and reviewed to confirm that potential participants meet all eligibility criteria. The investigator will maintain a screening log to record details of all participants screened and to confirm eligibility or record reasons for screening failure, as applicable.
- Procedures conducted as part of the participant's routine clinical management and obtained before signing of the ICF may be utilised for screening or baseline purposes provided the procedures met the protocol-specified criteria and were performed within the timeframe defined in the SoA.
- In the event of a significant study-continuity issue (eg, caused by a pandemic), alternate strategies for participant visits, assessments, medical device distribution and monitoring may be implemented by the investigator, as per local health authority/ethics requirements.

The study is using already collected data, except for personal apps and data collected through the medical devices.

Adverse Events (AEs) or Serious Adverse Events (SAEs) related to the AIDAVA prototype are not expected during this assessment study, as this is a Class 1 medical device supporting patients in managing and curating available data and there are no medical interventions during the assessment apart from collecting additional data.

For CVD patients, in case of medical device deficiency for the CVD use case, the potential risk is that a SMART risk score will not be properly computed. Physicians will calculate the score as well manually and can compare the calculations with the score that AIDAVA has provided; in any case no medical decisions will not be made based on AIDAVA score alone.

In case of a high SMART risk score detected during the assessment, the treating physician should use measures that include promoting a healthy lifestyle through behaviour changes, including nutrition, physical activity, relaxation training, weight management and smoking cessation programmes for resistant smokers. These would ideally help cope with the illness and improve adherence and cardiovascular outcome.

9. Statistical Considerations

The analysis and reporting will be done on all data from all participants at 3 points in time: before the evaluation starts (curator arm only for G0), after G1 evaluation (G1 report) and after G2 evaluation (G2 report).

9.1 Statistical Hypotheses

The primary objective is to demonstrate that G1 of the AIDAVA prototype is superior to the current situation in achieving data curation and publishing of personal health data; and that G2 is superior to G1. Improved efficiency will be measured through 4 endpoints i.e. M1 (usability of the tool), M2 (decreased time to curated data), M3 (high quality of resulting data), M4 (extraction of structured data from text).

- The 2 critical metrics are M2 (time) and M3 (quality).
- While important, **M1 (usability)** should be possible to improve (more training, increased explanation, ..) and the results of the evaluation will provide directions on how to improve.
- M4 (NLP performance) will improve with the introduction of new technologies (Large Language Models like ChatGPT and BARD) and is therefore less critical for the future of AIDAVA.

Thus, the null hypothesis to be tested in relation to the **primary estimand**¹⁷ is as follows.

• Null hypothesis (H0): The efficiency of data curation and publishing of personal health data is not different between G1 or G2 of the AIDAVA prototype and the current situation. There is no impact due to training on data curation.

vs.

- Alternative hypothesis (H1):
 - G1 of the AIDAVA prototype is more effective than the current situation with respect to the efficiency of data curation and publishing of personal health data and G2 is even more effective than G1.
 - The efficiency improvement is due mainly to the tool; some improvement is related to the training on data curation.

The null and alternative hypotheses corresponding to the secondary estimands are as follows:

Secondary objective for Breast Cancer Use Case:

- Null hypothesis: There is no difference with AIDAVA, to get an answer to specific queries on the BC registry across sites, in terms of accuracy and time.
- Alternative hypothesis (H2-BC): AIDAVA G1 provides correct answers on queries on the BC registries across sites (with an accuracy 90% or higher), while avoiding BC specialists (and supporting team) to spend time. G2 has similar or better results.

¹⁷ estimand (trial objective) is the target of estimation. In AIDAVA, the primary estimand is improved efficiency in data curation

Secondary objective for CVD specialists :

- Null hypothesis: There is no difference to compute SMART score for patients across sites, in terms of accuracy and time with AIDAVA.
- Alternative hypothesis (H2 CVD): AIDAVA G1 provides an accurate SMART score (accuracy of 80%+) on patients, across sites, without any time spent by CVD specialists. G2 has similar or better results.

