3.1. Primary endpoints

The **primary objective** of the assessment study is to compare the acceptance and the performance of the AIDAVA prototype versus existing practice, and between the 2 versions of the prototype. To this end, we propose to measure the following endpoints that will be recorded across sites.

Objective	Primary Endpoints
Metric 1. Evaluate acceptance by end users	Metric definition: Structured questionnaire (adapted from a System Usability Scale with additional questions such as I would recommend AIDAVA to my friend, colleague, or family member I am interested / ready to work with AIDAVA when available on the market I understand the purpose of data curation I am ready to spend the needed time to ensure proper data curation The curation process was perfect/acceptable/too long for me Measurement score (M1) through structured questionnaire (System Usability Scale - form) provided in REDCap
Metric 2. Measure	Metric definition
impact on workload for quality enhancement of data (including quality of the different curation tools)	 Compare time spent in curating data in G0 (current situation) G1 (generation 1 of the prototype) G2 (generation 2 of the prototype). Check the amount of data curated in the average time: are there more data being curated together with the ones needed to support the use case
	 Measurement For estimated time spent in curating (M2.1) User entry in dedicated "Curator form" (RedCap) For curators, when requesting an estimate for G0, it is important to ensure that curated data set have the same level of complexity as for G1 and G2 complexity: Extract a sample (synthetic data ?) to be curated including several data sources; Request existing registry stewards to provide a time to curate data up to insertion into registry (M2.2) System check "active" time of user to answer a query Amount of additional data elements are curated automatically computed (M2.3) How many data elements have been curated automatically by the systems (M2.4) How many data elements have required human interventions and been successful answered by the patients (i.e. answer provided to the question)

Objective	Primary Endpoints
	 (M2.5) How many data elements have required human interventions can not be answered by the patients and are sent to the curators (M2.6) How many data elements send to the curators did not get appropriate answer to finish the curation process

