Metric 3. Measure quality of data resulting from the data curation & publishing - in terms of their interoperability and reusability	 Metric definition: Data quality score measuring components related to the quality of the personal health knowledge graph and supporting its re-use. This includes dimensions such as volume (number of data items curated), completeness (number of missing items), consistency (number of consistency checks that fail), availability of context information (metadata).
	 Measurement: automatically computed by system at G1 and G2: System computes scores automatically ; formula are being defined in D4.6/Task 4.2 (due date Feb 2024)
Metric 4. Assess the quality/quantity of concepts that can be extracted from clinical narratives with different technologies	 Metric definition: Computed quality of the NLP concept extraction against the manually annotated data ("gold standard") Precision (M4.1): fraction of correct gold standard instances among the retrieved instances Recall (M4.2): fraction of the gold standard concepts that are successfully extracted
	 Measurement 0. Requires a manually annotated gold standard 1. Measure at G0 (current situation): measure # of concepts extracted for registry, manually – in limited time frame (few minutes) 2. Measure at G1 and G2: Precision/Recall for three different NLP systems a. The minimal-effort translation-based system developed for G1 b. The tools with novel DL models developed for G2 c. Measuring generalisation ability to new languages (at G2) The expected outcome is that (b) > (c) > (a). We will measure how well models trained of any two of the three languages (German, Dutch, Estonian) can generalise to the third language as a proxy for how well the overall system can adapt to new languages.

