9.2 Analysis Sets

Primary endpoint components

The analysis set will include all expert curators and patient participants and will take into account the primary data points (PDP) identified in yellow in the figure below across the 3 arms.

Primary Data Point	Generation	Arm	Description of measures (through RedCap Form and computed)		
PDP1	G0		M2.1 : Estimated time spent in curation per patient record (min)		
PDP2	G1	Expert Curator	M1: System Usability Score M2.1: Estimated time spent in curation per patient record (min)		
PDP3	G2		Same than for G1 - measured for G2		
PDP4	G1	G1 AND G2 users	 M1: System Usability Score M2: Time spent in for curation in min Estimated time in RedCap form (M2.1) Computed "active" time to answer queries (M2.2) Computed amount of data elements curated automatically by system (M2.3) requiring human intervention with answer from the patient (M2.4) 		

Primary Data Point	Generation	Arm	Description of measures (through RedCap Form and computed)
			 without answer the patient and requiring curator input (M2.5) without answer requested from curator but not successful (M2.6)
			M3: Computed data quality scores of curated record in terms of completeness, correctness, consistency and trustworthiness (as detailed in Task 4.6).
			 M4: Computed quality of the NLP concept extraction against the manually annotated data ("gold standard") Precision (M4.1) which measures the fraction of gold standard instances among the retrieved instances Recall (M4.2) which measures the fraction of the gold standard concepts that could successfully be retrieved
PDP5	G2		Same than PDP4 - for G2
PDP6	G1	G1 OR G2	Same than PDP4 - for G1
PDP7	G2	users	Same than PDP5 - for G2

Secondary endpoints

The analysis set will include all data users (BC specialists and CVD experts) and will take into account the secondary data points (SDP) identified in orange in the figure below across the patient arms. As indeed this is about reuse of data, after the curation process; there is no effect expected from the fact that patients did use G1 before G2 or not.

Secondary Data Point	Generation	Arm	Description of measures (through RedCap Form and computed)		
			Breast Cancer		

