9.3 Statistical Analyses

Three tests have be retained

- **Paired t-test**: statistical test that compares the means of two related groups, where each subject is measured at two different time points or under two different conditions. It is used to determine if there is a significant difference between the two groups.
- Mann-Whitney U test (unpaired t-test): non-parametric statistical test used to compare the medians of two independent groups. It is often used when the data are not normally distributed or when the sample sizes are small.
- Wilcoxon signed-rank test: non-parametric statistical hypothesis test used to compare two populations with two matched samples.

Primary Endpoint(s) Analysis

The endpoints are defined in Section 9.2 will be used to support the analysis

Computed	Description of measures	Test & meaning (per H1)			
	Population: Expert Curators				
E1	Difference between data points 1 and 2: E1.M2.1△ = M2.1@PDP1 - M2.1@PDP2 E1.M2.2△ = M2.2@PDP1 - M2.2@PDP2	Paired t-test H1: less time spent in curation in G1 than in G0 for expert curators			
E2	Difference between data points 2 and 3: E2.M1-Δ = M1@PDP2 - M1@PDP3	Paired t-test H1: G2 is more usable than G1 for expert curators			
	E2.M2.1∆ = M2.1@PDP2 - M2.1@PDP3 E2.M2.2∆ = M2.2@PDP2 - M2.2@PDP3	H1: less time spent in curation in G2 than in G1 for expert curators			
	Population:	Patients			
P1	Difference in data points 4 and 5 (i.e. difference between G1 and G2 for arm where patients used G1 AND G2)	Paired t-test (effect of system + training/experience from G1)			
	P1.M1- = M1@PDP4 - M1@PDP5	H1: G2 more usable than G1			
	P1.M2.x∆ = M2.x@PDP4 - M2.x@PDP5	H1: G2 requires less time for curation than G1 H1: G2 enables curation with less human intervention than G1			
	P1.M3-∆ = M3@PDP4 - M3@PDP5	H1: G2 provide same or higher quality than G1			
P2	Difference in data points 6 and 7 (i.e. difference between G1 and G2 for arm where patients used G1 OR G2)	Unpaired t-test (effect of system only)			
	P2.M1- = M1@PDP6 - M1@PDP7	H1: G2 more usable than G1			
	P2.M2.x∆ = M2.x@PDP6 - M2.x@PDP7	H1: G2 requires less time for curation than G1 H1: G2 enable curation with less human intervention than G1			
	Ρ2.Μ3-Δ = M3@PDP6 - M3@PDP7	H1: G2 provide same or higher quality than G1			

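### The primary claim that G1 beats current practice spans M1–M4, but only estimated curation time (M2.1) in expert curators has a usable G0 value, and contrast E1.M2.2 cannot be computed

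*Protocol*

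**What the plan says.** Section 9.1 opens with the aim: "The primary objective is to demonstrate that G1 of the AIDAVA prototype is superior to the current situation in achieving data curation and publishing". It adds that G2 is to be superior to G1, and it names the measures: "Improved efficiency will be measured through 4 endpoints i.e. M1 (usability of the tool), M2 (decreased time to curated data"), followed by M3 (data quality) and M4 (extraction from text). It then ranks them: "The 2 critical metrics are M2 (time) and M3 (quality"). Section 3.1 sets the same scope, namely to "compare the acceptance and the performance of the AIDAVA prototype versus existing practice, and between the 2 versions of the prototype". The synopsis lists all four metrics under a primary comparison of G0, G1 and G2.

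The measurement plan is narrower:

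- The opening of Section 9 places the first reporting point "before the evaluation starts (curator arm only for G0").
- In Section 9.2, PDP1 is the only primary G0 data point. Its single entry is M2.1: "Estimated time spent in curation per patient record (min").
- Section 3.1 says M3 is "automatically computed by system at G1 and G2".
- Section 9.3 has one primary row that uses G0, row E1. It holds two differences, one on M2.1 and one on M2.2. The second is "M2.2@PDP1 - M2.2@PDP2".

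**The concern.** The objective, the data points and the contrasts do not match. Section 9.1 promises superiority over current practice in terms that include data quality, one of the two critical metrics, yet the plan collects no quality value for current practice.

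The risk lies in what may be concluded. If E1.M2.1 comes out in favour of G1, Section 9.1 as worded lets it be read as support for the whole alternative hypothesis, quality included. Curation that became faster but produced worse data than current practice would go unnoticed, because no primary contrast compares quality with G0.

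Separately, Section 9.3 specifies a paired test on a quantity that has no G0 measurement.

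**Working it through.** The plan gives no figure to reproduce here. The check compares Sections 3.1, 9.2 and 9.3.

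**Step 1. Which primary metrics have a G0 value that can be compared with G1?**

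- **M1 (usability):** first listed at PDP2, which is G1. It scores the AIDAVA system, so it has no counterpart without the system. No G0 value.
- **M2 (time):** M2.1 is at PDP1 (G0) and PDP2 (G1), both in expert curators. Usable.
- **M3 (quality):** computed by the system at G1 and G2 and listed only in the patient data points PDP4 to PDP7. No G0 value.
- **M4 (text extraction):** Section 3.1 does plan a G0 measure, a count of concepts extracted by hand in a few minutes. At G1 and G2 the measures are precision and recall against a gold standard. The count is on a different scale, is absent from PDP1, and appears in no contrast in Section 9.3.

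Result: 1 of 4 primary metrics, and 1 of the 2 critical ones, can be compared with G0.

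**Step 2. Does each expert-curator contrast have its inputs in Section 9.2?** PDP1 lists M2.1. PDP2 lists M1 and M2.1. PDP3 repeats PDP2 for G2.

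| Contrast | First data point | Second data point |
|---|---|---|
| E1.M2.1 (G0 to G1) | listed | listed |
| E1.M2.2 (G0 to G1) | not listed | not listed |
| E2.M1 (G1 to G2) | listed | listed |
| E2.M2.1 (G1 to G2) | listed | listed |
| E2.M2.2 (G1 to G2) | not listed | not listed |

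The two M2.2 gaps differ in kind. Section 9.2 defines M2.2 as the computed active time to answer queries. At G0 there is no system to pose or time a query, so E1.M2.2 cannot be computed however the table is edited. At G1 and G2 curators do answer queries in the system, so E2.M2.2 can be obtained once M2.2 is listed for them.

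Result: of the two primary contrasts that use G0, one (E1.M2.1) can be computed.

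**Step 3. On how many people does the remaining contrast rest?** The table in Section 9.4 gives 3 sites × 3 curators = 9, while the text of the same section says 12. As context only, and on my assumption of a two-sided 5% level and 80% power (the protocol states neither), a paired t-test needs a standardised mean difference of about 1.07 with 9 curators, or about 0.89 with 12.

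**The case against.** The best defence is that the narrowing already exists. The footnote to Section 9.1 defines the primary estimand as improved efficiency in data curation. The four endpoints are introduced after two aims taken together, so not every endpoint need serve both. The hypothesis attached to row E1 concerns curation time in expert curators only. This shows that the authors of Section 9.3 probably meant a time comparison. It does not remove the conflict, because Section 9.1 itself says efficiency is measured through all four endpoints and calls quality critical, and the synopsis sets G0 against all four metrics.

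One might also say that M2.2 at G0 is the time requested from registry stewards, since the M2 labels in Section 3.1 run together. Section 9.2 settles this: M2.2 is the computed active time.

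Several stronger readings are tempting, and the documents do not support them:

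- **That only one of about 39 primary contrasts can be computed against G0.** That total counts M2.x as six measures and M3 as one (2 + 3 + 8 + 8 + 10 + 8 = 39). Of these, 39 − 2 = 37 never involve G0 by design. The relevant fraction is one of two.
- **That the absence of any patient at G0 is a defect.** Restricting G0 to the curator arm is a stated design choice, and patients have no G0 curation task.
- **That E2.M2.2 is also impossible.** It is a listing omission. Section 3.1 describes the measure for a user, which includes curators.
- **That the trial never compares AIDAVA with manual work on patient data.** The secondary endpoints do so for SMART score time and accuracy and for the breast cancer queries. They supply no M3 value at G0, so they do not rescue the primary quality claim.

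**Conclusion.** The point holds as an inconsistency within the protocol that changes what the trial may conclude. Superiority of G1 over the current situation can be tested on estimated curation time in expert curators and on no other primary measure. M3, a critical metric, has no G0 value. E1.M2.2 is specified but cannot be computed.

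This rests on reading PDP1 as the complete list of primary G0 measures and on the definition of M2.2 in Section 9.2. It does not depend on a statistical analysis plan: one could clarify the wording, but it could not supply G0 values that the protocol does not collect. The comparisons of G2 with G1 on M1, M3 and M4 are untouched.

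**What to change.** - In Section 9.1, Section 3.1 and the synopsis, limit the hypothesis of G1 against the current situation to estimated curation time (M2.1) in expert curators. State that M1, M3 and M4 are compared between G2 and G1 only, and that a positive E1.M2.1 is not evidence of better data quality than current practice.
- Delete E1.M2.2 from Section 9.3.
- Add M2.2 to the PDP2 and PDP3 entries in Section 9.2, or delete E2.M2.2.

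Scoring a G0 record with the M3 formulas is not a ready substitute. Section 3.1 asks the stewards for a time, on a sample that may be synthetic, and describes no curated G0 output. M3 scores a knowledge graph, and none is described at G0.

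The cost is wording and a few table entries, with no new data collection. The real price is a narrower primary claim.

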Difference in data points 1 and 2 (i.e. difference between G1 and G2 across all patients) U1.TBCx- Δ = TBCx@SDP1 - TBCx@SDP2 U1.EBCx- Δ = EBCx@PSP1 - EBCx@SDP2 U1.ACCx- Δ = ACCx@SDP1 - ACCx@SDP2	Paired t-test H1: G2 has more (or same) accuracy than G1 while keeping the same time saving and duration
Cardiovascu	lar
	Descriptive Statistics around performance in G1 of the AIDAVA system (e.g. mean,)
Difference in data points 1 and 2 (i.e. difference between G1 and G2 across all patients) U1.TCVD- Δ = TCVD@SDP1 - TCVD@SDP2	Paired t-test H1: G2 has more (or same) accuracy than G1 while keeping the same time saving
	Description of measures Breast Canc Difference in data points 0 and 1 (i.e. difference between G0 and G1 across a sample of 15 patients) U0.TBCx- Δ = TBCx@SDP0 - TBCx@SDPA U0.EBCx- Δ = EBCx@SDP0 - EBCx@SDP1 U0.ACCx- Δ = ACCx@SDP0 - ACCx@SDP1 Difference in data points 1 and 2 (i.e. difference between G1 and G2 across all patients) U1.TBCx- Δ = TBCx@SDP1 - TBCx@SDP2 U1.EBCx- Δ = EBCx@PSP1 - EBCx@SDP2 U1.ACCx- Δ = ACCx@SDP1 - ACCx@SDP2 Cardiovascu Difference in data points 1 and 2 (i.e. difference between G1 and G2 across all patients) U1.TCVD- Δ = TCVD@SDP1 - TCVD@SDP2 U1.ACCyD- Δ = ACVD@SDP1 - ACVD@SDP2 U1.ACCyD- Δ = ACVD@SDP1 - ACVD@SDP2

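### The primary null hypothesis sets G2 against current practice, but Section 9.3 lists no G0–G2 contrast; for curator time the only route is a two-link chain that leaves the question untested if either link misses

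*Protocol*

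**What the plan says.** Section 9.1 gives the primary null hypothesis as efficiency of curation and publishing that "is not different between G1 or G2 of the AIDAVA prototype and the current situation". Metric 2 in Section 3.1 is defined in the same three-way form: "Compare time spent in curating data in G0 (current situation) G1 (generation 1 of the prototype) G2 (generation 2 of the prototype". The synopsis (Section 1.1) also describes the primary comparison as one without AIDAVA, with G1 and with G2.

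The objective and the alternative hypothesis in Section 9.1 are written as a chain. The objective begins "The primary objective is to demonstrate that G1 of the AIDAVA prototype is superior to the current situation" and goes on to G2 over G1; the alternative adds that "G2 is even more effective than G1".

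The opening of Section 9 limits the baseline to one group: "before the evaluation starts (curator arm only for G0". In Section 9.2 the G0 data point (PDP1) holds a single measure, "M2.1 : Estimated time spent in curation per patient record (min". The same measure is taken from expert curators at G1 (PDP2) and at G2 (PDP3).

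For expert curators, Section 9.3 lists E1 (PDP1 against PDP2) and E2, described as "Difference between data points 2 and 3". The breast cancer analyses follow the same pattern: G0 against G1, then "Difference in data points 1 and 2 (i.e. difference between G1 and G2 across all patients".

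**The concern.** The null hypothesis names a comparison that the list of contrasts does not contain. This is not detail that can be left to a later analysis plan, because the protocol itself enumerates the contrasts and the list does not match its own hypothesis.

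G2 against today's way of working is what a hospital would want to know about the later version, and curation time is one of the two metrics that Section 9.1 calls critical. Section 2 says that G1 orchestrates existing tools while G2 adds the novel language-processing and human–AI modules. It is therefore plausible that most of the gain appears only at G2, or that the gain is spread over both steps. In either case a real advantage of G2 over current practice could go unsupported although the data to show it had been collected.

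**Working it through.** **Contrasts set against generations (Section 9.3)**

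| Contrast | Population | Compares |
|---|---|---|
| E1 | Expert curators | G0–G1 |
| E2 | Expert curators | G1–G2 |
| P1, P2, A3 | Patients | G1–G2 |
| A4 | Patients | P1 against P2, both G1–G2 |
| A1, A2 | Patients | Descriptive, one generation each |
| Breast cancer, first | Data users | G0–G1 |
| Breast cancer, second | Data users | G1–G2 |
| CVD | Data users | G1–G2 |

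Contrasts using G0 among the primary analyses: one (E1). Contrasts of G0 with G2: none, primary or secondary.

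**What the data points allow (Sections 3.1 and 9.2)**

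- M2.1: expert curators at PDP1 (G0), PDP2 (G1) and PDP3 (G2). A paired G0–G2 difference can be formed.
- M1: no G0 value.
- M3: computed at G1 and G2 only, so no G0 value.
- M4: Section 3.1 describes a manual count at G0, but it is not in PDP1 and has no contrast.

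For a curator measured at all three points, (PDP1 − PDP2) + (PDP2 − PDP3) = PDP1 − PDP3, so the missing contrast is the sum of the two listed ones.

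**Chain against direct contrast**

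The protocol states no alpha, power, SD or effect size for these tests, so there is no figure of its own to reproduce. The assumptions here are a paired t-test at two-sided 5% and equal correlation between the three measurements. All three paired differences then have the same SD, taken as 1. Section 9.4 gives 12 curators in the text and 9 in the table (3 sites × 3), so both are shown.

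For a mean paired difference d (in SD), the noncentrality is d√n on n − 1 degrees of freedom. Example with n = 9 and a step of 0.5:

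- E1 or E2 alone: 0.5 × 3 = 1.5, power 26%.
- Direct G0–G2: d = 0.5 + 0.5 = 1.0, noncentrality 3.0, power 75%.
- Both E1 and E2: about 3% by simulation. This is below 0.26 × 0.26 = 7% because the G1 measurement enters the two differences with opposite sign, so they are negatively correlated.

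| Assumed gains (G0→G1, G1→G2) | n = 9: both links | n = 9: direct | n = 12: both links | n = 12: direct |
|---|---|---|---|---|
| 0.5, 0.5 | 3% | 75% | 7% | 88% |
| 0.6, 0.6 | 8% | 88% | 16% | 96% |
| 0.8, 0.8 | 26% | 99% | 47% | >99% |
| 1, 0 | 1% | 75% | 2% | 88% |
| 0, 1 | 1% | 75% | 2% | 88% |

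For a single paired contrast, 80% power needs a mean difference of about 1.07 SD with 9 curators or 0.89 SD with 12.

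**The case against.** The strongest reply is that the objective and the alternative hypothesis are a chain, G1 over G0 and G2 over G1, and that E1 and E2 match it link for link. If both succeed, G2 over G0 follows. That is right. A reader might infer that the study cannot say whether G2 beats current practice; the documents do not support this. The contrast is unplanned, not impossible, and a fully successful chain would carry the conclusion.

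A reader might also infer that a slow G1 could make G2 look good with nothing in the plan to expose it. That goes too far as well. If G1 is 0.8 SD slower than G0 and G2 merely returns to the G0 level, E2 is significant in 56% of studies with 9 curators, but E1 shows a significant slowdown in 56% too, and both links never succeed together in practice. A false claim would need E2 to be read alone, against the stated alternative. What stands is that seeing the slowdown still does not answer the G2–G0 question.

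Three further points limit the scope:

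- Section 3.2.2 compares physician scoring time with AIDAVA at G1 and at G2, so a human comparison at G2 exists for that secondary endpoint.
- The breast cancer gap matters less. Section 9.1 claims only similar or better results for G2, and Section 3.2.1 expects query time to be the same in G1 and G2. SDP0 lists effort (EBCx), but the G0 form shown in Section 10.3.4 has fields for TBC1 to TBC3 only.
- The step sizes and correlations are assumptions. Equal steps favour the direct contrast because they give it twice the effect of either link. The two rows with the whole gain at one generation do not, and the chain succeeds there in only 1–2% of studies.

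**Conclusion.** The point holds as a mismatch between the null hypothesis and the listed contrasts, with a practical consequence for curator time. G2 against the current situation is in the hypothesis and in Metric 2, and it has no contrast in Section 9.3. The chain of E1 and E2 supports G2 over G0 only when both succeed. Under the stated assumptions that happens in 3–26% of studies with 9 curators and 7–47% with 12 for equal steps of 0.5 to 0.8 SD, where a direct contrast succeeds in 75–99% and in 88% to over 99%. These percentages illustrate the gap and do not predict the study's power.

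The point reaches M2.1 only. For M1 and M3, which include the other critical metric, no G0 value exists. The null hypothesis cannot be tested against the current situation on them for either generation, and an added contrast cannot change that.

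**What to change.** 1. Add to the expert curator rows of Section 9.3: E3.M2.1 = M2.1@PDP1 − M2.1@PDP3, paired, same curators. Name it as the test of G2 against the current situation on curator time, and base any such claim on it.
2. Reword the null hypothesis in Section 9.1 so that the comparison with the current situation is confined to measures with a G0 value. State that M1 and M3 have none.
3. Optionally add SDP0 against SDP2 for TBCx in the breast cancer table, and for EBCx only if effort is actually collected at G0.

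Restating the null hypothesis as the chain G1 against G0 and G2 against G1 would remove the inconsistency, but it would still leave G2 against current practice untested whenever one link misses.

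The curator row uses measurements already planned at PDP1 and PDP3, so no new data are needed. The downside is one more test per endpoint.
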